9.1.12 Treatment after Initial Evidence of Radiologic Disease Progression

Immunotherapy may produce antitumor effects by potentiating endogenous cancerspecific immune response. The response patterns seen with such an approach may extend beyond the typical time course of responses seen with cytotoxic agents and can manifest as a clinical response after an initial increase on tumor burden or even the appearance of new lesions. If radiological imaging shows PD, subjects may continue on study with the option of continuing treatment, provided there is:

- No deterioration in ECOG performance status
- Absence of signs and symptoms (including worsening of laboratory values) indicating disease progression
- Absence of rapid progression of disease
- Absence of progressive tumor at critical anatomical sites (e.g., cord compression) requiring urgent alternative medical intervention

Tumor assessment should be repeated ≥4 weeks later to confirm PD. If repeat imaging shows a reduction of in the tumor burden demonstrating CR, PR or SD compared to the initial scan, treatments may be continued or resumed. If repeat imaging shows continued progression of disease, subjects will be discontinued from study therapy, unless the basis for the PD assessment is enlarged tumor-draining lymph nodes in the presence of a target tumor reduction. In determining whether or not tumor burden has increased or decreased, investigators should consider all target lesions as well as non-target lesions. If the repeat imaging confirms initially documented PD but shows no evidence of further tumor progression, subjects should be discontinued from the study treatment.

10 INVESTIGATIONAL DRUG PRODUCT

The Investigator shall take responsibility for and shall take all steps to maintain appropriate records and ensure appropriate supply, storage, handling, distribution and usage of investigational product in accordance with the protocol and any applicable laws and regulations.

ADXS11-001 will be supplied free of charge by Advaxis, Inc.

10.1 Packaging and Labeling

Clinical supplies will be affixed with a clinical label in accordance with regulatory requirements.

This trial is open-label; therefore, the subject, the trial site personnel, the sponsor and/or designee are not blinded to treatment. Drug identity (name, strength) is included in the label text; random code/disclosure envelopes or lists are not provided.

10.1.1 Storage and Handling Requirements

Clinical supplies must be stored in a secure, limited-access location under the storage conditions specified on the label.

Receipt and dispensing of trial medication must be recorded by an authorized person at

the trial site.

Clinical supplies may not be used for any purpose other than that stated in the protocol.

10.1.2 Returns and Reconciliation

The Investigator is responsible for keeping accurate records of the clinical supplies received from Advaxis or designee, the amount dispensed to subjects and the amount remaining at the conclusion of the trial.

Upon completion or termination of the study, all unused and/or partially used investigational product will be destroyed at the site per institutional policy.

10.1.3 Destruction of ADXS11-001

It will be the investigator's responsibility to arrange for disposal of all empty containers, provided that procedures for proper disposal have been established according to applicable federal, state, and local regulations and institutional guidelines and procedures, and provided that appropriate records of disposal are kept.

If ADXS11-001 is destroyed at the site, it will be the investigator's responsibility to ensure that procedures for proper disposal have been established according to applicable regulations, guidelines, and institutional procedures and that:

- Written authorization for disposal/destruction has been granted by Advaxis
- Arrangements have been made for the disposal
- Appropriate records of the disposal have been documented

10.2 ADXS11-001 Records at Investigational Site

It will be the responsibility of the Investigator to ensure that a current record of ADXS11-001 disposition is maintained at each study site where ADXS11-001 is inventoried and disposed. Records or logs must comply with applicable regulations and guidelines, and should minimally include:

- The amount received and placed in storage area
- The amount currently in storage area
- The label identification, lot, or batch number
- Dates and initials of person responsible for each ADXS11-001 inventory entry/movement
- The amount dispensed to and returned by each subject, including unique subject identifiers
- The amount transferred to another area for dispensing or storage
- Non-study disposition (e.g., lost, wasted, broken)
- The amount destroyed at study site, if applicable

10.2.1 Safety Precautions

ADXS11-001 is a live attenuated strain of Listeria monocytogenes (Lm) that has been attenuated such that it is cleared by severe combined immunodeficiency (SCID) mice lacking cellular immunity and gamma interferon knock-out mice lacking adaptive immunity. It has also been altered such that it is impossible for it to recombine with wild-type Lm.

Wild type *Listeria* is Gram-positive, non-spore-forming, facultative bacilli that are hemolytic and catalase-positive. It is a naturally occurring bacterium that is present in the environment and is known to cause illness in some people when they eat foods contaminated with *Lm*. Although healthy adults and children can contract a wild-type *Listeria* infection, they do not usually become seriously ill. People at risk of severe illness from wild-type *Listeria* are pregnant women, newborns, and persons with impaired immune function.

Even though ADXS11-001 is non-pathogenic, all *Lm* species are classified as according to the BMBL 5th Edition. Universal precautions and institutional guidelines should be used when handling investigational drugs and human specimens. Except for the transmission of mother to fetus, human-to-human transmission

of Lm is not known to occur.[19] Shedding studies completed in Phase 1 demonstrated that, in the absence of antibiotics, ADXS11-001 was rapidly cleared from the blood with no Lm detected in the blood of any subject beyond 48 hours post-dosing, and no Lm was detected in the urine and feces in any subject at the highest dose of ADXS11-001 tested (1 x 10^{10} CFU) [11].

Based on the mechanism of action of ADXS11-001 and the inability of *Lm* to be transferred from human-to-human, there is no need for subjects who receive ADXS11-001 to avoid contact with people who are elderly, pregnant, newborns, or have weakened immune systems.

Precautions as stated in the BMBL 5th Edition include:

Wild-type L. monocytogenes poses a potential hazard to laboratory personnel. The Gram-positive, non-spore-forming, aerobic bacilli are hemolytic and catalase-positive. Bacteria have been isolated from soil, dust, human food, animals, and asymptomatic humans. Most cases of listeriosis have arisen from eating contaminated food products, most notably soft cheeses, raw meat, and unwashed raw vegetables. Although healthy adults and children can contract a Listeria infection, they do not usually become seriously ill. At risk of severe illness are pregnant women, newborns, and persons with impaired immune function.

Laboratory Hazards: Wild-type Lm may be ubiquitous in the environment and may be found in feces, cerebrospinal fluid (CSF), and blood, as well as food and environmental materials. Ingestion is the most common mode of exposure, but wild-type Listeria can also cause eye and skin infections following a direct exposure. Wild-type Lm infections in pregnant women occur most often in the third trimester and may precipitate labor. Transplacental transmission of Lm poses a grave risk to the fetus and may result in disseminated abscesses contributing to a mortality rate of nearly 100%.

Recommended Precautions: practices, containment equipment, and facilities are recommended for activities with clinical specimens and cultures known or suspected to contain the agent. Biopsy specimens must be fixed immediately by dropping the specimen in formaldehyde solution. Gloves and eye protection should be worn while handling the agent. Pregnant women who work with Listeria monocytogenes in the clinical or research laboratory setting should be fully informed of the potential hazards associated with the organism, including potential risks to the fetus.

11 CLINICAL SAFETY MANAGEMENT

11.1 ADXS11-001 Pretreatment Prophylaxis Regimen

Mild to moderate flu-like symptoms and cytokine release symptoms (e.g., constitutional symptoms such as fever, chills, rigors, fatigue, headache, nausea, vomiting, tachycardia, shortness of breath, hypotension and rash) are commonly seen and typically occur 2-4 hours after ADXS11-001 infusion and often resolve within 12-24 hours. Prophylactic medications are intended to reduce the inflammatory response. Subjects should receive the following pretreatment prophylaxis regimen.

IV Fluid Hydration:

• Normal saline (e.g., 500 mL over 30 minutes)

Premedication Regimen:

- Antihistamine PO or IV (e.g. diphenhydramine 25 mg or equivalent), once
- NSAIDs PO (e.g., naproxen 220 mg or ibuprofen, 400 mg), once
- Antiemetic PO or IV (e.g., promethazine or ondansetron), once
- Histamine H2-receptor antagonist PO or IV (e.g., famotidine 20 mg or equivalent), once

Pretreatment medication should be given on the day of dosing and completed at least prior to the start of the assigned study treatment. Additional NSAID doses and antiemetic administration should be given per label or package insert post initial administration on Day 1 and Day 2, as needed. The prescribed dosage of the selected NSAID and antiemetic will be at the discretion of the Investigator.

Do not substitute acetaminophen for the selected NSAID for prophylactic treatment since acetaminophen does not have similar anti-inflammatory properties that could ameliorate cytokine release symptoms.

11.3 Administration of ADXS11-001

11.2 Step-Up Regimen for ADXS11-001 Pre-Dose Treatment Prophylaxis

Antiemetics such as promethazine or ondansetron will continue to be given as described above in Section 11.1. Thus, subjects will leave the study site with doses of the NSAID and antiemetic to take later in the day, as appropriate.

11.4 Supportive Care Guidelines

11.4.1 Cytokine Release Symptoms

Cytokine release symptoms are a constellation of inflammatory symptoms resulting from cytokine elevations associated with T cell engagement and proliferation. Symptoms related to cytokine release may include constitutional symptoms such as fever, chills, rigors, fatigue, headache, nausea, vomiting, rash, tachycardia, hypotension and shortness of breath which usually presents several hours after the infusion and lasts for up to 24 hours. These symptoms are caused by an increase in cytokines such as TNF α , IFN γ and IL-6, all of which have been shown to occur after ADXS11-001 administration, resulting from the body's immune response to the therapy. Although, symptoms are often Grade 1-2 and transient, resolving with symptomatic management within 30 minutes to 1 hour, in rare instances (\sim 1%) Grade 3-4 hypotension has been seen. Therefore, close monitoring of blood pressure is strongly recommended at baseline, and during the post-infusion period. Increased levels of IL-6have been strongly associated with capillary leak which manifests as hypotension due to the cytokines involved. We have observed elevated IL-6 levels after infusion of ADXS11-001, with peak levels occurring 2-4 hours after infusion. Emerging evidence indicates that IL-6 antagonists, such as tocilizumab, have demonstrated good results in treating cytokine-induced hypotension [20-23] and are therefore recommended for cases of severe hypotension refractory to supportive care (e.g., fluids and/or pressors).

The management of cytokine release symptoms and guidelines for subsequent treatment for subjects who have experienced these AEs are shown in Table 9.

Table 9 Recommended Management Guidelines for Adverse Events Associated with Cytokine Release

Toxicity	NCI CTCAE Grade or Severity	Treatment	Modification for Subsequent infusions
Hypotension	1 Mild	Supportive care	Increase pretreatment IV fluids (e.g., 500 ml -1L normal saline)
All other cytokine release symptoms (e.g. chills, rigors, fever, nausea, vomiting)	1	Supportive care	No modification
Hypotension	2 Moderate	 Fluids and 1 dose of pressor (e.g. 0.3 mg epinephrine IM) Increase monitoring of vital signs If hypotension persist for more than one hour consider low dose corticosteroids (e.g. hydrocortisone 100 mg IV over 30 seconds 	 Extend infusion time to 2 hours. Increase pretreatment IV fluids (e.g. 500 ml -1L normal saline) Incorporate Glucocorticoid- Hydrocortisone or equivalent- 50 mg, IV, as premedication
All other cytokine release symptoms (e.g. chills, rigors, fever, nausea, vomiting)	2	Appropriate supportive care measure	 Extend infusion time to 2 hours. Consider increasing doses of prophylactic medications
Hypotension	3 Severe	 Fluids, high dose pressors (e.g. Dopamine 10 μg/kg/min) +1 dose tocilizumab*(4mg/kg over 1 hour) If hypotension worsens or is unresponsive to above measures, administer corticosteroids If the subject's condition does not improve or stabilize within 24 hours of the tocilizumab dose, administration of a second dose of tocilizumab +/- corticosteroids should be considered. 	Discuss with Sponsor

Toxicity	NCI CTCAE Grade or Severity	Treatment	Modification for Subsequent infusions
All other cytokine release symptoms (e.g. chills, rigors, fever, nausea, vomiting)	3	Appropriate supportive care measures	 Extend infusion time to 2 hours. Consider increasing doses of prophylactic dose of NSAID, or antiemetic as appropriate
Hypotension/ Organ toxicity, mechanical ventilation	4 Life threatening	 Vigilant supportive care Fluids High dose pressors, Tocilizumab (4mg/kg over 1 hour) +/- corticosteroids (hydrocortisone 100 mg IV infused over 30 seconds administered every 2 hours until symptoms resolve to <grade 1)<="" li=""> </grade>	Permanently discontinue

^{*} Tocilizumab is a humanized, immunoglobulin G1k (IgG1k) anti-human IL-6R mAb approved for treatment of adult subjects with moderately to severely active rheumatoid arthritis (RA) who have had an inadequate response to Disease-Modifying Anti-Rheumatic Drugs (DMARDs), for the treatment of active polyarticular juvenile idiopathic arthritis (PJIA), and active systemic juvenile idiopathic arthritis (SJIA) in subjects 2 years of age and older. Tocilizumab works by preventing IL-6 binding to both cell-associated and soluble IL-6Rs. Although, it is not indicated for the treatment of cytokine release symptoms emerging clinical experience at several institutions has concluded that tocilizumab is an effective treatment for severe or life-threatening cytokine release symptoms. [20-23]

11.4.2 Nausea/vomiting

Nausea and vomiting should be treated aggressively. In addition to the prophylactic antiemetic therapy subjects receive prior to each infusion, consideration should be given to subsequent administration of antiemetic therapy every 8 hours, as needed according to standard institutional practice. Subjects should also be strongly encouraged to maintain liberal oral fluid intake.

11.5 Management of Infusion Reactions

While there is some overlap between infusion reactions symptoms and cytokine release symptoms, infusion reactions symptoms typically occur during the infusion, while cytokine release symptoms typically occur after the infusion and are mediated by a different mechanism of action. Signs/symptoms of infusion reactions may include: allergic reaction/hypersensitivity (including drug fever); arthralgia (joint pain); bronchospasm; cough; dizziness; dyspnea (shortness of breath); fatigue (asthenia, lethargy, malaise); headache; hypertension; hypotension; myalgia (muscle pain); nausea; pruritic/itching; rash/ desquamation; rigors/chills; sweating (diaphoresis); tachycardia; tumor pain (onset or exacerbation of tumor pain due to treatment); urticaria (hives, welts, wheals); and vomiting.

Table 10 below shows the management guidelines for subjects who experience an infusion reaction associated with administration of ADXS11-001.

Table 10 Recommended Management Guidelines for Infusion Reactions

NCI CTCAE Grade	Management
Grade 1	
Mild reaction; infusion interruption not indicated; intervention not indicated	Increase monitoring of vital signs as medically indicated until the subject is deemed medically stable in the opinion of the Investigator.
Grade 2	
Requires infusion interruption but responds promptly to symptomatic treatment (e.g., antihistamines, NSAIDS, narcotics, IV fluids); prophylactic medications indicated for ≤24 hrs.	Stop Infusion and monitor symptoms. Additional appropriate medical therapy may include but is not limited to:
	the subject is deemed medically stable in the opinion of the Investigator. If symptoms resolve within one hour of stopping drug infusion, the infusion may be restarted at 50% of the original infusion rate. Otherwise dosing will be held until symptoms resolve and the subject should be premedicated for the next scheduled dose.
Grades 3 or 4	
Grade 3: Prolonged (i.e., not rapidly responsive to symptomatic medication and/or brief interruption of infusion); recurrence of symptoms following initial improvement; hospitalization indicated for other clinical sequelae (e.g., renal impairment, pulmonary infiltrates) Grade 4: Life-threatening; pressor or ventilatory support indicated	 Stop Infusion. Additional appropriate medical therapy may include but is not limited to:
	6. Subjects who experience a Grade 4 reaction should be permanently discontinued from study. Subjects who experience a grade 3 reaction may be discontinued. Discussion with the Sponsor is recommended

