6 STUDY DESIGN AND TREATMENT PLAN

In this Phase 1, open-label, multi-center study, subjects with persistent, metastatic or recurrent squamous cell or non-squamous cell carcinoma, adenosquamous carcinoma, or adenocarcinoma of the cervix who have failed conventional therapy will receive the highest dose tolerated of ADXS11-001 infused intravenously (IV)

(± 10 minutes) with overall infusion volume of 250 mL on Day 1 of Weeks 1, 4, 7, and 10 of each 12-week cycle. Subjects must complete the prophylactic regimen at least prior to each ADXS11-001 infusion (as noted in Section 11.1) to mitigate and manage the potential immune response seen with immunotherapy administration.

Subjects who experience a DLT during the dose escalation portion of the study or experience events described as a DLT in any subsequent treatment cycle will be discontinued from study treatment. However, if the subject who experienced a DLT shows significant response to ADXS11-001, they may be eligible to receive ADXS11-001 at a lower dose level for subsequent doses and cycles following discussion and agreement between the Investigator and Sponsor. See Section 6.1 Dose Limiting Toxicity Criteria for definition of DLT.

The treatment to be used in this trial is outlined below in Table 4. Trial treatment should begin on the day of randomization or as close as possible to the date on which the treatment level is allocated/assigned.

Details on the dose calculation, preparation and administration are provided in the Pharmacy Manual.

Table 4 Trial Treatment

[figure not shown]
Dose Level	ADX11-001	Schedule
1	5 x 10 ⁹ CFU	Q3wks
2	$1 \times 10^{10} \text{CFU}$	Q3wks
-1	$1 \times 10^9 \text{CFU}$	Q3wks

ADXS11-001 will be given as a 3 weeks in repeating 12-week cycles

250 mL IV infusion every

A standard 3 + 3 design will be used in the dose escalation portion of the study. ADXS11-001 will be administered in sequential cohorts of 3-6 subjects, with a minimum of 48 hours between initial dosing for each of the first 3 subjects treated at each dose level. The first cohort will enroll a minimum of 3 subjects, according to a standard 3 + 3 design shown schematically in Figure 1.

Figure 1 3+3 Design Schematic

- Subjects in the first cohort will receive a dose of ADXS11-001 5 x 10⁹ CFU (Dose Level 1).
- If no DLTs are experienced in the 28 day DLT observation period at Dose Level 1, the next dose level of ADXS11-001 1 x 10¹⁰ CFU (Dose Level 2) will be explored.

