DLTs will only be assessed during the first 28 days in cycle 1 (See Section 6.1, Dose Limiting Toxicity Criteria, for DLT definition). Transient hypotension which may require IV fluids for management is an expected event that subjects may experience with ADXS11-001 infusions. Subjects with signs of cytokine release symptoms ≥Grade 3 (per CTCAE v 4.03) that persist for more than 24 hours despite symptomatic treatment, will be judged to have a DLT. Blood cultures will not be obtained on a routine basis but will be collected in subjects who have persistent fever 24 hours after the end of ADXS11-001 infusion. Subjects will receive a 7-day course of either oral 80 mg trimethoprim / 400 mg sulfamethoxazole once daily or 160 mg trimethoprim / 800 mg sulfamethoxazole (DS) 3 times over the course of the 7 days. Subjects with known allergy to sulfa drugs may receive ampicillin 500 mg 4 times daily for 7 days beginning on Day 4 (approximately 72) hours) after each study treatment infusion. A subject who experiences a fever (CTCAE Grade 1 or greater) 24 hours following the completion of ADXS11-001 infusion should be started on NSAIDS, hydration and other appropriate measures to treat the fever. In the event that the fever persists or worsens 48 hours following the completion of ADXS11-001 infusion then oral or broad spectrum IV antibiotics should be considered based on the subject's medical condition. If the fever remains unresponsive to oral/IV antibiotics 72 hours following the completion of the infusion then a blood culture should be obtained to evaluate for listeremia and determine the appropriate treatment course for the subject. Study cycles can be repeated at the RP2D (or less) for each subject until a discontinuation criterion is met. Criteria include documented disease progression, intolerable side effects not resolved with dose reduction or change in pre-medications, or the completion of 1 cycle of treatment post observation of complete response per RECIST 1.1 and immunerelated RECIST criteria (irCR).

Safety will be assessed by comparing treatment-related AEs, changes in physical examinations, vital sign measurements, and laboratory abnormalities.

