6.1 Dose Limiting Toxicity Criteria

DLT will be evaluated during the first 28 days of the first cycle during the dose escalation portion of the trial. All toxicities will be graded using CTCAE v 4.03. The occurrence of any of the following toxicities will be considered a DLT, if judged by the Investigator to be possibly, probably or definitely related to therapy. Treatment modifications for DLT are shown in Table 11.

Hematologic:

- 1. Grade 4 hematologic toxicity.
- 2. Febrile Neutropenia, defined as absolute neutrophil count (ANC) < 1000/mm³ with a single temperature of >38.3° C (101° F) or a sustained temperature of >38° C (100.4° F) for more than 1 hour.
- 3. Grade 3 thrombocytopenia lasting >72 hours.
- 4. Grade 4 thrombocytopenia.

Non-Hematologic:

1. ≥Grade 3 non-hematologic toxicity, (excluding nausea, vomiting and/or diarrhea lasting <3 days and reversible with medical intervention).

- 2. Grade 3 non hematologic laboratory values, (excluding transient Grade 3 laboratory value abnormalities, hematologic and non-hematologic, reversible within 5 days and without necessity for medical intervention).
- 3. Listeremia: positive blood cultures(s) along with persistent (for 72 hours post dose) symptoms consistent with listeremia (e.g., fever and muscle aches, often preceded by diarrhea or other gastrointestinal symptoms).
- 4. \(\geq \) Grade 3 flu-like symptoms or cytokine release symptoms that persist for >24 hours after study treatment administration despite symptomatic treatment.

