11.6.2 ADXS11-001 Treatment Alterations

Subjects who experience a DLT during the dose escalation portion of the study or experience events described as a DLT in any subsequent treatment cycle will be discontinued from study treatment. However, if the subject who experienced a DLT shows significant response to ADXS11-001, they may be eligible to receive ADXS11-001 at a lower dose level for subsequent doses and cycles following discussion and agreement between the Investigator and Sponsor. See Section 6.1 Dose Limiting Toxicity Criteria for definition of DLT.

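### Table 10 makes stopping optional after a Grade 3 infusion reaction, while Sections 6 and 11.6.2 require it when the reaction is dose-limiting under Section 6.1

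*Combined protocol and SAP*

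**What the plan says.** Four places in the protocol bear on what happens after a Grade 3 infusion reaction.

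- **Table 10, Section 11.5.** Item 6 of the Grade 3/4 cell directs permanent discontinuation at Grade 4. For the lower grade it says "Subjects who experience a grade 3 reaction may be discontinued", and discussion with the Sponsor is recommended. Table 10 describes Grade 3 as a reaction that is prolonged, that recurs after initial improvement, or that calls for hospitalization.
- **Section 6.1.** Provided the Investigator judges the event at least possibly related, non-hematologic item 1 makes a DLT of "≥Grade 3 non-hematologic toxicity, (excluding nausea, vomiting and/or diarrhea lasting <3 days and reversible with medical intervention". Item 4 is narrower and covers "Grade 3 flu-like symptoms or cytokine release symptoms that persist for >24 hours after study treatment administration despite symptomatic treatment". The section adds: "Treatment modifications for DLT are shown in Table 11".
- **Sections 6 and 11.6.2.** In the same words, both say that subjects who have a DLT in dose escalation or who "experience events described as a DLT in any subsequent treatment cycle will be discontinued from study treatment". The one exception is that "if the subject who experienced a DLT shows significant response to ADXS11-001, they may be eligible to receive ADXS11-001 at a lower dose level", following discussion and agreement between Investigator and Sponsor.
- **Table 11, Section 11.6.1.** Its non-hematologic row leaves out DLTs and cytokine release symptoms. The text above the table says the dose is not to be reduced or increased.

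**The concern.** A clinician managing a reaction at the infusion chair will look at Table 10. It firmly requires stopping at Grade 4 and leaves stopping open at Grade 3. It mentions neither DLT status, nor response, nor a lower dose. If the same reaction is a DLT, Section 11.6.2 has already taken the decision: study treatment stops unless the subject is a significant responder who goes to a lower dose by agreement.

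The matter at stake is re-dosing safety and consistency between sites. A site following Table 10 could give the same dose again to a non-responder who has just had a prolonged or recurrent reaction. Another site following 11.6.2 would stop that subject. Each could cite the protocol.

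**Working it through.** The plan gives no figure on this point, so there is nothing to reproduce. The check sets the rules side by side and then applies the dosing calendar.

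**1. Can a Grade 3 infusion reaction be a DLT?** Yes. Item 1 of Section 6.1 excludes only short, reversible nausea, vomiting and diarrhea.

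**2. Does the 24-hour allowance in item 4 take these reactions out?** Only in part. Section 11.5 lists 20 infusion reaction signs.
- Nine also appear in the cytokine release list of Section 11.4.1: dyspnea, fatigue, headache, hypotension, nausea, rash, rigors/chills, tachycardia and vomiting.
- Myalgia corresponds to the body ache in the flu-like list of Section 11.6, so 9 + 1 = 10 overlap.
- 20 − 10 = 10 do not overlap, among them bronchospasm, urticaria and allergic reaction. Counting drug fever and arthralgia as overlap leaves 10 − 2 = 8.

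The lists are illustrative, so this shows only that item 4 does not clearly reach these signs. Section 11.5 also says that infusion reactions arise by a different mechanism.

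**3. Which periods does the mandatory stop cover?** Section 6 states that "DLTs will only be assessed during the first 28 days in cycle 1", and Section 6.1 confines DLT evaluation to dose escalation. Section 11.6.2 then adds DLT-type events in subsequent cycles. Cycle 1 after day 28 and cycle 1 of the expansion cohort are outside both, so the optional wording in Table 10 contradicts nothing there.

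**4. One case under both rules.** Take a related Grade 3 bronchospasm, not rapidly responsive to medication, in a dose escalation subject within the first 28 days.

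| | Table 10, item 6 | Sections 6 and 11.6.2 |
|---|---|---|
| Stop study treatment? | Optional | Required |
| Condition for continuing | None stated | Significant response |
| Dose if continued | Not stated | Lower dose level |
| Sponsor role | Discussion recommended | Agreement needed |

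**5. How much dosing is in question within cycle 1?** Infusions are given "on Day 1 of Weeks 1, 4, 7, and 10 of each 12-week cycle". Day 1 of week w is day 7(w − 1) + 1, which gives days 1, 22, 43 and 64. Two of the four nominal infusions fall within 28 days. After a qualifying reaction at infusion 1, Table 10 leaves up to 4 − 1 = 3 further cycle 1 infusions open; at infusion 2, up to 4 − 2 = 2. Section 11.6.2 allows none unless its exception applies. The first scheduled scan is at Week 12, day 7 × 11 + 1 = 78, or days 71 to 85 with the one-week allowance. The last nominal infusion, on day 64, comes before it. Scheduled imaging therefore cannot show the response that the exception requires before these infusions are due.

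**6. Does another section settle it?** Section 6.1 points to Table 11, but the non-hematologic row there excludes DLTs, so the pointer gives no rule for these events. Table 12 (Section 13.6) requires advance approval by the clinical monitor in two situations: rechallenge after a serious event that the product may have caused, and re-exposure that adds potential significant risk. It is an approval step and does not mandate stopping. The readable text does not say which rule takes precedence.

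**The case against.** The strongest reply is that the rules can be read together. The title of Table 10 calls it recommended guidance, and it covers every Grade 3 infusion reaction, many of which are not DLTs. Section 11.6.2 is specific and mandatory, and a site that stops a DLT subject complies with both. Table 11 excludes non-hematologic DLTs and 11.6.2 follows directly, which suggests where the authors meant those events to go. This is a fair account of the likely intent. It does not cure the text, because Table 10 has no cross-reference and the pointer in Section 6.1 leads elsewhere.

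A second reply is that re-dosing is already controlled. Table 12 demands prior approval in the situations described above. A reaction that leads to inpatient admission is also an SAE, reportable within 24 hours under Section 13.7.1. Escalation decisions rest with the Sponsor in consultation with the Investigators, in cohorts of 3 to 6, so a DLT subject is unlikely to be re-dosed unnoticed. This stands as partial mitigation. A reader might infer from Table 10 alone that nothing stands between a site and re-dosing, and Table 12 rules that out.

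A third reply concerns the wording. The Grade 4 sentence in item 6 speaks of leaving the study, so the Grade 3 sentence may do the same. On that reading, treatment stops under 11.6.2 and only study withdrawal is discretionary, which is no conflict. Items 1 to 5 of the cell are not legible and might bear on further dosing. Both points stand and limit confidence.

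**Conclusion.** The inconsistency is real but limited to related Grade 3 infusion reactions that meet Section 6.1 in the periods covered by 11.6.2. There Table 10 permits what 11.6.2 forbids: re-dosing a non-responder, or re-dosing anyone at the same dose. For other Grade 3 reactions the optional wording is correct. Those include cycle 1 after day 28, expansion cohort cycle 1, brief reversible nausea or vomiting, and possibly cytokine-type symptoms lasting 24 hours or less.

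Two stronger conclusions are tempting and are not supported. A reader might infer that dose escalation is compromised. It is not: what counts as a DLT is fixed by Section 6.1, and the 3+3 counts are the same whichever rule governs later dosing. A reader might also apply an assumed reaction rate to the 6 to 12 dose escalation subjects and report how many are affected. The readable text gives no rate for Grade 3 infusion reactions; the figure of about 1% in Section 11.4.1 is for Grade 3-4 hypotension from cytokine release. Nor does a reaction by itself mean conflicting care, since a site would also have to follow Table 10 over 11.6.2 and the checks above would have to let re-dosing through. The number affected cannot be estimated from the documents.

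The sponsor should correct the text. Confidence is moderate: the conclusion assumes that the Grade 3 sentence refers to study treatment and that the illegible items contain no cross-reference to 11.6.2.

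**What to change.** In Table 10, replace the Grade 3 sentence of item 6 with: *A Grade 3 reaction that meets Section 6.1 is handled under Section 11.6.2 (discontinue study treatment, with only the 11.6.2 lower-dose exception); other Grade 3 reactions may be discontinued from study treatment after discussion with the Sponsor.* This also settles whether study or study treatment is meant.

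In Section 6.1, point non-hematologic DLTs to Section 11.6.2. Limit the new pointer to those events. Grade 4 hematologic toxicity is also a DLT, and the hematologic row of Table 11 allows restart after resolution whereas 11.6.2 requires stopping. That separate mismatch is not settled by this change and should not be made worse by giving one event two pointers.

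The cost is one sentence and one cross-reference, with no new stopping rule. A few subjects may lose re-treatment that 11.6.2 already forbids, and Sponsor discussion of the remaining Grade 3 reactions becomes an expected step rather than a recommendation. Whether mandatory stopping should extend to cycle 1 after day 28 or to expansion cohort cycle 1 is a separate decision for the sponsor.
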